[Redacted text line]

[Redacted text line]

[Redacted text block]

1. **Statement of Purpose:** State the scientific aim(s) of the study, or the hypotheses to be tested.

The aim of this study is to examine the effect of mHealth tools on antiretroviral (ART) adherence and persistence among HIV-infected individuals with co-occurring cocaine use disorders (CUDs). The specific aims are:

- (1) To conduct qualitative assessments using focus groups of people living with HIV (PLH) who use cocaine and healthcare providers that will assess the acceptability, feasibility, facilitators and barriers of implementing mHealth interventions; and will aid in developing the final design and content of both automated and clinician feedback in preparation for designing a pilot feasibility study.
- (2) To conduct a 12-week pilot feasibility RCT among PLH with co-occurring CUDs that will examine the impact of mHealth tools (cellular-enabled smart pill boxes and cell phones) and feedback (no feedback vs. automated feedback vs. automated + clinician feedback vs. vs. automated + text-reminder from a social network) on primary (ART adherence and persistence) and secondary outcomes (HIV viral suppression, cocaine use, retention in HIV care).

The hypotheses include:

- (1) Patients with automated feedback + clinician feedback will have higher ART adherence and persistence than patients with only automated feedback and patients with no feedback.
- (2) Patients with automated feedback + clinician feedback will have improved HIV outcomes including lower changes in log₁₀ HIV-1 RNA levels, higher CD4 counts and higher rates of retention in care, compared to patients with only automated feedback and patients with no feedback.
- (3) Patients with automated feedback + clinician feedback will have decreased cocaine use compared to patients with only automated feedback and patients with no feedback.
- (4) Patients with automated feedback + text-reminder from a social network will have higher ART adherence and persistence than patients with only automated feedback and patients with no feedback.
- (5) Patients with automated feedback + text-reminder from a social network will have improved HIV outcomes including lower changes in log₁₀ HIV-1 RNA levels, higher CD4 counts and higher rates of retention in care, compared to patients with only automated feedback and patients with no feedback.

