- (6) Patients with automated feedback + text-reminder from a social network will have decreased cocaine use compared to patients with only automated feedback and patients with no feedback.
- (7) There is statistically significant difference between a patient's ART adherence and persistence and HIV outcomes when their designated social network member lives inside vs outside patient's activity space.

2. **Background:** Describe the background information that led to the plan for this project. Provide references to support the expectation of obtaining useful scientific data.

Antiretroviral therapy (ART) is extremely effective at reducing morbidity and mortality, and reducing HIV transmission among people living with HIV (PLH).^{1,2} Clinical effectiveness, however, is largely dependent on patients' ART adherence and persistence.³⁻⁹ ART non-adherence and non-persistence substantially reduce viral suppression (VS)¹⁰ and increase HIV transmission risk to others.¹¹⁻¹⁵ Substance use disorders (SUDs) further contribute to poor health outcomes, primarily by reducing ART adherence and persistence.¹⁶⁻²⁰ Cocaine use disorders (CUDs), in particular, result in a number of poor HIV treatment outcomes, including decreased retention in care, poor ART adherence and persistence, low VS, and accelerated HIV progression.²¹⁻²⁸ Considering the high prevalence of CUDs among PLH²⁹⁻³⁴ and the absence of effective medication-assisted therapies (MAT) for treating CUDs, innovative strategies of improving ART adherence in this group are urgently needed.

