mHealth interventions can be valuable for PLH since they make it possible to have a tightly woven network of coordinated care by providing real-time data about dosing reminders,^{63,64} medication intake,^{44,46} and solicitation of care.⁶² The inclusion of tailored automated feedback has been especially successful at promoting positive health outcomes for other conditions,⁶⁵⁻⁶⁷ yet has not been compared to personalized clinician feedback. Despite their immense potential, the acceptability, feasibility and effectiveness of mHealth tools have not yet been developed and tested among PLH with co-occurring CUDs. Moreover, mHealth interventions have not optimized the integration of feedback to determine what type of feedback improves outcomes. Thus, this study will provide crucial preliminary information necessary to determine acceptability, study design and implementation procedures for conducting the most optimal RCT using a quadruple (patient-mHealth-clinician-social network) relationship for improving ART adherence and persistence in PLH with CUDs.

Significance

- A. **ART Access, Adherence and Persistence:** Among the ~1.2 million PLH in the U.S., ART adherence and persistence is problematic for many, resulting in too few patients achieving VS. In the absence of VS, HIV transmission and mortality among PLH increase.^{1,2,68} Virological

failure, either through suboptimal adherence (not taking ART as prescribed)^{36,69,70} or non-persistence (gaps in continuous ART treatment),^{18,71} results in development of resistance mutations, increased mortality⁷², and complicated care.^{3-9,16-19,73} For PLH with co-occurring SUDs, there are additional negative health outcomes; active drug use is associated with clinicians not prescribing or delaying prescribing ART.⁷⁴ When ART is optimized, it also improves outcomes for other co-morbid conditions.¹⁷ A meta-analysis has documented that patients with SUDs who receive adherence support, adhere to ART similarly to non-drug users.⁷⁵ Adherence support, however, must be provided using a strong theoretical model with documented effectiveness and in this case, be effective with SUDs.

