Innovation: Significance and innovation are high because of the combination of several factors – (1) the focus on PLH with CUDs to promote ART adherence; (2) incorporation of qualitative assessment using focus groups among HIV+ cocaine users to examine their willingness to incorporate mHealth interventions and among healthcare providers in order to understand their interest in deploying mHealth ART interventions for patients with CUDs; , and among selected social network members to understand their interest in becoming ‘health-buddy’ and providing long-term and sustainable support for healthcare; (3) the intervention to be developed and pilot-tested involves two mHealth-based **reminders** (via cellular-enabled smart pill boxes and cell phones), and three types of **feedback** (automated electronic feedback based on adherence from smart pill boxes, and clinician feedback based on a weekly smartphone-based survey and weekly text-reminder from a designated social network member) – each of which has separately shown to improve ART adherence, persistence and VS in PLH but not in drug users; . In addition, prior studies have used network-driven interventions for HIV prevention but not for ART adherence, persistence, and VS in PLH and definitely not by combining mhealth tools with social relations (4) the comparison of automated electronic and personalized clinician and text-reminder from a social network member feedback as part of the intervention, especially since feedback and communication loops have been under-utilized in interventions in PLH with SUDs;^{109,110} (5) extension of our established use of feedback using the Information-Motivation-Behavioral Skills (IMB) conceptual framework for adherence using a computer interface (LifeWindows project),¹¹¹ but now applied to mHealth to promote adherence; and (6) a multidisciplinary group of researchers experienced in addiction medicine, HIV, intervention development particularly adherence interventions, behavioral science, Geographic Information System (GIS), social network analysis (SNA) and mHealth who have already created CDC-recommended ART adherence interventions for drug users. Thus, this

study is uniquely positioned to provide crucial information necessary to develop a mHealth tool-enabled intervention strategy for PLH and CUDs.

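### The four feedback conditions are set against one another in Aim 2, but the hypotheses and the analysis leave out two of the six pairwise contrasts: clinician versus social-network feedback (C−D) and automated versus no feedback (B−A)

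*Combined protocol and SAP*

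**What the plan says.** All references are to the combined protocol and SAP. Letters follow the order in which the conditions are listed: A no feedback, B automated, C automated plus clinician, D automated plus social-network text.

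- **Statement of Purpose, Aim 2** puts the four conditions side by side: "feedback (no feedback vs. automated feedback vs. automated + clinician feedback vs. vs. automated + text-reminder from a social network". The Research Plan repeats this twice.
- **Background, Innovation item (4)** lists as a feature of the study "the comparison of automated electronic and personalized clinician and text-reminder from a social network member feedback as part of the intervention".
- **Background** says of existing work that "mHealth interventions have not optimized the integration of feedback to determine what type of feedback improves outcomes". It then says that this study will help "determine acceptability, study design and implementation procedures for conducting the most optimal RCT".
- **Hypotheses 1 to 3** concern C. Hypothesis 1 says that C "will have higher ART adherence and persistence than patients with only automated feedback and patients with no feedback". Hypothesis 2 does the same for HIV outcomes, and hypothesis 3 says that C "will have decreased cocaine use compared to patients with only automated feedback and patients with no feedback".
- **Hypotheses 4 to 6** repeat the pattern for D against B and A. Hypothesis 4 begins "Patients with automated feedback + text-reminder from a social network will have higher ART adherence and persistence than patients with only automated feedback".
- **Hypothesis 7** is a comparison inside D only.
- **Statistical Considerations, Aim 2** gives an overall mixed-design analysis with three intervention conditions and three follow-ups, then MANCOVA with follow-up ANCOVA, or a GLM. It names no pairwise arm contrast.

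**The concern.** The aim poses a four-way question, and the hypotheses answer part of it. No hypothesis sets the clinician arm against the social-network arm, and none asks whether automated feedback, which B, C and D share, does better than none. The analysis section does not make up for this.

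The C−D gap matters because the Background stresses that new adherence interventions should need less money and fewer staff, and the two add-ons differ on that point. C uses a nurse funded by the study. D uses a text from a network member's own phone. If no C−D estimate is planned, the obvious substitute is to see which add-on reached significance against B. That does not compare C with D, and with unequal arms it favours the larger one.

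The B−A gap matters for interpretation. C−A and D−A each combine the automated component with an add-on. C−B and D−B isolate the add-ons, but no named contrast isolates the automated component.

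**Working it through.** **Inputs.** Arm sizes of 20 in each of A, B and C and 30 in D (Sample Size and Power Calculations). The documents give no effect size, SD, power or dropout rate, so results are in SD units. Two-sided alpha of 0.05 for arm contrasts is my assumption, and so is the 20% loss used below.

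**The plan's own figure.** 3 × 20 + 30 = 90, which matches the stated total. It does not match the 1:1:1:1 allocation under Randomization, which gives 90 / 4 = 22.5 per arm.

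**Coverage of contrasts.** Four arms give 4 × 3 / 2 = 6 pairs.

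| Pair | Named in |
|---|---|
| C−A, C−B | Hypotheses 1, 2, 3 |
| D−A, D−B | Hypotheses 4, 5, 6 |
| C−D | none |
| B−A | none |

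**What full success would settle.** There are 4! = 24 strict orderings of the arms. Requiring C and D each to beat both A and B leaves four: C>D>A>B, C>D>B>A, D>C>A>B and D>C>B>A. A and B are ruled out as best. The order of C and D, and the order of A and B, stay open.

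**Precision if the contrasts are added.** SE = SD × √(1/n₁ + 1/n₂), half-width = t(0.975, n₁+n₂−2) × SE.

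- C−D, 20 vs 30: SE = √(1/20 + 1/30) = 0.289 SD, half-width 0.58 SD.
- B−A, 20 vs 20: SE = √(1/20 + 1/20) = 0.316 SD, half-width 0.64 SD.
- The planned D−A and D−B have the same arm sizes as C−D, and the planned C−A and C−B the same as B−A, so precision is equal.
- With about 86 residual degrees of freedom (90 − 4) from a four-arm model, the half-widths are 0.57 and 0.63 SD.
- With 20% loss (16 vs 24 and 16 vs 16): 0.65 and 0.72 SD.
- With near-equal allocation (22 vs 23), C−D: 0.60 SD.

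**Power if they were tested** (normal approximation).

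| True difference (SD) | 0.2 | 0.3 | 0.5 | 0.8 |
|---|---|---|---|---|
| C−D | 10% | 18% | 41% | 79% |
| B−A | 9% | 16% | 35% | 72% |

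**Why comparing significance across arms misleads.** Suppose C and D each truly improve on B by 0.5 SD. Power is 35% for C−B (20 vs 20) and 41% for D−B (30 vs 20). Identical effects have different chances of reaching significance.

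**Why the C−D point estimate cannot pick the arm.** The chance that its sign favours the better arm is Φ(d / 0.289). At d = 0.2 SD this is about 76%, so the wrong arm looks better about 24% of the time.

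**The case against.** The case on the other side has several parts.

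*Purpose.* A reader might infer from the Background that choosing between feedback types is the trial's purpose. The documents do not say so. The sentence quoted from the Background describes a gap in earlier work, and the next one asks for information on acceptability, design and procedures for a later RCT built on a relationship that includes both clinician and social network. The sample-size section speaks of refining procedures and preparing a larger trial. No section promises to select C or D or gives a rule for doing so. This stands. The point rests on Aim 2 and Innovation item (4), which do present a comparison of the conditions.

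*Information already there.* Fully positive results would rule out A and B and show that each add-on helps. In a linear model, C−D = (C−B) − (D−B) and B−A = (C−A) − (C−B), so no data are lost. This also stands. What the plan lacks is a stated contrast with its CI, and a CI for C−D cannot be read off the separate intervals for C−B and D−B because they share arm B.

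*Pilot size.* Neither contrast can be a useful test at 20 to 30 per arm. True, but the four named contrasts have the same precision, so size does not explain leaving these two out. It is a reason to report estimates rather than tests.

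*Meaning of B−A.* The Intervention section describes automated medication reminders without limiting them to particular arms. Until the difference between A and B is written down, B−A may not isolate the automated component. This stands and is carried into the fix.

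**Conclusion.** The point holds as a mismatch between the stated comparison and the planned contrasts. Four of six pairs are named, and C−D and B−A are not. The analysis section names none and is written for three conditions. Adding the two estimates needs no new data. Their half-widths are about 0.58 and 0.64 SD before attrition.

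Three stronger readings are not supported. Full success would not leave the trial unable to say anything about feedback type, since it would narrow the field to C and D. B−A does not help in choosing between C and D; it concerns the automated component only. And the documents say that the nurse is study-funded but do not say whether network members are paid, so a cost contrast should not be pressed beyond that.

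The figures assume the 20/20/20/30 sizes, two-sided 0.05, a roughly normal outcome at one time point and no covariate adjustment. Section 12 expects a GLM for adherence, where the contrasts would be on that model's scale.

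**What to change.** In Statistical Considerations, Aim 2:

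1. Replace the three-condition model with a four-condition one. The trial has four arms, so this is needed in any case.
2. Add a sentence such as: In addition to the contrasts in hypotheses 1 to 6, the four-arm model will report C minus D and B minus A for adherence and persistence, with 95% CIs, as exploratory estimates without significance claims.
3. State what separates arm A from arm B, including which arms receive the automated reminders. Until then, do not read B−A as the effect of the automated component.
4. State that any choice of arm for the later RCT will not rest on the C−D point estimate alone. Report that estimate with its CI, next to feasibility and acceptability.

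The stated arm sizes and the 1:1:1:1 allocation should also be reconciled, although this hardly changes C−D precision (0.58 against 0.60 SD).

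The cost is a few sentences and no extra participants or measurements. The downside is two more imprecise estimates to report.

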All 90 participants for the pilot RCT study will be recruited from New Haven-area community HIV clinics, the Ryan White Consortium, and substance abuse treatment (SAT) centers. As indicated in the gender and minority inclusion statement, women and minorities will be represented in all sites of recruitment. The minimum age is 18 years of age, thus children 18-21 years old will be eligible for participation.

2.A. **Recruitment Procedures:** Similar to the recruitment procedure for the FGs IRB-approved flyers containing a toll-free number will be posted in numerous venues such as community SAT centers and HIV care clinics. Centers that have collaborated with us before and have been prime sites of recruitment include the Nathan Hale Clinic, Haelen Center, Hill Health Center, Central Medical Unit, Fair Haven Clinic, most of which are included in the Ryan White consortium. Due to our continued presence in New Haven through the implementation of several treatment programs and clinical trials, we are confident of being able to recruit participants for the pilot RCT. If enrollment is insufficient, we will post an announcement in “Did You Know?” – an electronic newsletter managed by [name], Director of the New England AIDS Education and Training Center - Local Performance Site - that is disseminated regularly to New Haven-area clinics. This will help us reach all the local area HIV clinics that can refer potential participants to our study.

In addition to the above-mentioned recruitment sources, we will also be able to recruit from the Community Health Care Van (CHCV). The CHCV, a 36-foot van is equipped with two exam rooms, a counseling/phlebotomy room and a waiting area. The staff has developed strategic liaisons with patients and providers throughout the community and is capable of connecting researchers with potential HIV-infected patients with co-occurring substance abuse issues.

2.B. **Screening Procedure:** The initial screening eligibility criteria will include the following: (1) HIV+, (2) self-reported cocaine use in the past 6 months, and (4) speaks English or Spanish. If an individual meets the initial screening criteria, they will be invited to meet with a research assistant (RA) to determine if they fulfill all the necessary eligibility criteria to be included in the study.

Eligibility Criteria:

Inclusion Criteria	Exclusion Criteria

- | | |
|---|--|

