| 
 • Age \geq 18 years • Clinic-confirmed HIV diagnosis • Currently prescribed or eligible for ART • Currently has insurance • Self-reported cocaine use ever • Willing and able to use a cell phone and blister pack for the 12-week intervention | 
 • Unable to provide informed consent • Verbally or physically threatening to research staff • Unable to communicate in either English or Spanish |
|---|--|

2.C. Informed Consent and Enrollment Procedures: All participants must be able to provide informed consent to be enrolled in the study. The RA will obtain informed consent and then explain the purposes, protocol, expectations, and possible risks and benefits of the study.

2.D. Randomization: Although a specific randomization process is not required for pilot RCTs, we want to ensure that crucial covariates that might influence our outcomes are controlled for a priori, especially given the modest sample size proposed in this pilot. Since it has been well-documented that individuals with underlying mental illness experience worse outcomes, we will minimally stratify based on the presence or absence of neurocognitive impairment. Randomization will be 1:1:1:1 to patients receiving either no feedback, automated feedback or automated + clinician feedback, and automated feedback + text-reminder from a social network.

2.E. Study Procedures:

1. Baseline Interview: After the informed consent procedure, participants will be asked to sign a medical release of information (ROI) to allow research staff to confirm self-reports of HIV status, medication prescription and healthcare utilization and to be able to communicate with the participants' clinical providers. The RA will then conduct the baseline interview consisting of various self-reported measures including demographic information, health care status, medical history, standardized measures for drug use and mental illness, and Information Motivation Behavioral (IMB) constructs for adherence. Participants will also undergo phlebotomy.

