Aim 1 (Focus Groups): We will conduct six FGs, four with HIV+ cocaine users and two with healthcare providers, comprised of 6-8 persons each. For the PLH FGs, we will recruit PLH who primarily use cocaine, from clinical care and community outreach programs in New Haven, CT. Of the four PLH FGs, one will consist solely of men and one solely of women in order to address possible gender differences. Eligibility criteria will be: a) ≥ 18 years; (b) speaks English or Spanish; c) HIV+; d) self-reported cocaine use in the previous 30 days; and e) able to give informed consent. For the two healthcare provider FGs, we will recruit physicians, nurses, clinic supervisors, and substance abuse counselors from HIV clinics. We will target representation from the 5 HIV clinics in New Haven.

Aim 2 (Pilot Feasibility Study): We will recruit 90 participants from HIV care clinics and drug treatment programs in New Haven. Eligibility criteria will include: 1) clinic-confirmed HIV diagnosis; 2) ≥ 18 years; 3) prescribed or eligible (clinician willing to prescribe) for ART; 4) currently have insurance coverage; 5) self-reported cocaine use in the past 6 months; and 6) and willing and able to use an electronic pill box and blister pack for study duration. This will be a 16-week study with a 12-week intervention and 4-week post-intervention observation period.

Sample Size and Power Calculations: The literature suggests that effect size calculations may not be appropriate for pilot RCTs.¹¹⁵ Thus, based on a review of pilot studies that have ranged in sample size from 12 per group¹¹⁶⁻¹¹⁸ to 9%-50%^{119,120} of the proposed larger RCT's sample size (generally 30 per arm); we propose to enroll 20 participants for groups A, B, and C. For Group D, we propose to enroll 30 participants so that hypotheses #7 (There is statistically significant difference between a patient's ART adherence and persistence and HIV outcomes when their designated social network member lives inside vs outside patient's activity space) can be tested. Therefore, a total of 90 study participants for the pilot feasibility RCT is proposed. This sample size is appropriate in order to refine study procedures, develop a final intervention manual and prepare for a future large-scale RCT.

NOTE: Is this research proposal designed to enroll children who are wards of the state as potential subjects? Yes No (If yes, see Instructions section VII #4 for further requirements)

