- e. Using the framework of structural equation modeling, we will identify the moderating and/or mediating effects of spatial (activity space and neighborhood levels) and non-spatial data (individual and interpersonal) covariates on the primary and secondary outcomes.

A comparative analysis will be conducted to contrast the model performance (R², AIC, and RMSE) of two mediation/moderation models with the primary (ART adherence) and a secondary (HIV viral suppression) outcome: 1) with social network metrics and b) with spatial-social network metrics (calculated in step#a).

SECTION VII: RECRUITMENT/CONSENT AND ASSENT PROCEDURES

1. Targeted Enrollment: Give the number of subjects:

a. targeted for enrollment at Yale for this protocol ____

Aim 1 (Focus Groups): 42 (30 PLH cocaine users; 12 healthcare providers)

Aim 2 (Pilot Feasibility Study): 90 PLH with co-occurring CUD

b. If this is a multi-site study, give the total number of subjects targeted across all sites ____

2. Indicate recruitment methods below. Attach copies of any recruitment materials that will be used.

- | | | |
|--|---|-------------------------------------|
|  Flyers |  Internet/Web Postings |  Radio |
|  Posters |  Mass E-mail Solicitation |  Telephone |
|  Letter |  Departmental/Center Website |  Television |
|  Medical Record Review |  Departmental/Center Research Boards |  Newspaper |
|  Departmental/Center Newsletters |  Web-Based Clinical Trial Registries | |
|  YCCI Recruitment database |  Clinicaltrials.gov Registry (do not send materials to HIC) | |
|  Other (describe): | | |

Upon funding of this study, flyers will be created.

3. Recruitment Procedures:

- a. Describe how potential subjects will be identified.
- b. Describe how potential subjects are contacted.
- c. Who is recruiting potential subjects?

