Aim 2 (Pilot Feasibility Study): Yale IRB-approved fliers will be used to help with recruitment for the RCT and the drug treatment counselors will also assist in recruitment of participants. When recruiting participants from venues, participants will be briefly told about the study and if they want to learn more about it, recruiters will hand out a contact information card to call into the study site. No information will be collected from them at this time so they may choose to not to call into the site or if they do call in and want to come in for consenting, information is still not collected and they may decline to come in. Participants will be provided an informed consent form that will be approved through the Yale University School of Medicine Institutional Review Board (IRB). The participant will be read the consent form verbatim and will be asked if they would like to participate in the study or not. The consent form will outline the agreement to participate in this research study. Participants will indicate consent by signing and dating the informed consent form. All patients will be reminded that their refusal to participate will not negatively affect their relationship with Yale University, local SAT or hospital facilities, their ability to continue in drug treatment, or their ability to obtain medical services from area clinics in the future. They will also be able to decline or take more time to think about it. If they agree, they will be asked to sign the consent form. They may choose to withdraw from the study at any point.

In addition, the following process of consent is going to be followed for the designated social network member for the fourth arm intervention (TRIDENT): a) after randomized to the 4th arm, the RAs and/or the Project Coordinator will ask the participant to call his/her designated social network member, b) the participant will explain the study details from an information sheet to the designee. At this stage the RAs and/or the Project Coordinator will also help in explaining the role

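### Section 2.D randomises 1:1:1:1, but the sample-size paragraph needs 20/20/20/30 of 90; followed as written, arm D gets about 22 or 23, not the 30 set for hypothesis 7

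*Combined protocol and SAP*

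**What the plan says.** The randomisation section (2.D) gives equal allocation: "Randomization will be 1:1:1:1 to patients receiving either no feedback" or one of three feedback conditions, the fourth arm being automated feedback plus a social-network text reminder. It adds one stratification factor with two levels: "we will minimally stratify based on the presence or absence of neurocognitive impairment". It gives no block size or other restriction on allocation.

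The Sample Size and Power Calculations paragraph (under Subject Population) plans unequal arms: "we propose to enroll 20 participants for groups A, B, and C. For Group D, we propose to enroll 30 participants". The reason given for the larger group D is to allow a test of hypothesis 7, which compares patients whose designated network member lives inside their activity space with those whose member lives outside it. The paragraph concludes: "Therefore, a total of 90 study participants for the pilot feasibility RCT is proposed".

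The same total appears in two other places. The opening of Specific Aim 2 says "All 90 participants for the pilot RCT study will be recruited", and Targeted Enrollment (Section VII, item 1) lists "90 PLH with co-occurring CUD".

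The consent section (Section VII, item 9) describes what happens to participants "after randomized to the 4th arm", so entry to group D is by randomisation. The document mentions no unequal ratio, no cap on arms A to C, no later enrolment phase for D and no non-randomised top-up.

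**The concern.** The allocation ratio and the planned arm sizes are both operative instructions, and they disagree. Whoever prepares the allocation list from 2.D will produce four arms of 22 or 23.

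Two things are at stake:

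- **Hypothesis 7.** It is a comparison within arm D, and it is the only stated reason for making D larger. The stated ratio removes the extra participants.
- **An improvised remedy.** Staff who want to honour the planned sizes under a 1:1:1:1 list could close A, B and C at 20 and send everyone after that to D. Those late assignments would be fully predictable and would have no concurrent controls. That would weaken the comparisons of D with no feedback and with automated feedback alone in hypotheses 4 to 6. The document does not describe this procedure; it is a possible result of the contradiction.

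**Working it through.** **Inputs from the document.** Ratio 1:1:1:1 (2.D). Planned sizes 20, 20, 20 and 30 (sample-size paragraph; 20 in each of A to C follows from the total). Total 90 (stated three times). Two strata (2.D). No power, significance level, effect size or inside/outside split is given for hypothesis 7.

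**1. The plan's own total.** 3 × 20 + 30 = 90. It reproduces.

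**2. What the stated ratio gives.**
- Expected size per arm: 90/4 = 22.5.
- Shortfall in D: (30 − 22.5)/30 = 25%.
- Total needed for 30 in D at 1:1:1:1: 4 × 30 = 120.
- Total at 20 per arm: 4 × 20 = 80. Neither equals 90.

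**3. Could D reach 30 by chance?**
- Simple randomisation: the D count is Binomial(90, 0.25), with SD √(90 × 0.25 × 0.75) = 4.1 and P(D ≥ 30) = 0.047.
- Permuted blocks within two strata (block sizes assumed): over every possible split of 90 between the strata, D lies in 21–24 for blocks of 4 and in 20–24 for blocks of 8. Thirty is out of reach.

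**4. Effect on hypothesis 7.** Assumed: two-sided 5% t-test, 80% power, even inside/outside split. The detectable standardised difference d is the value at which a noncentral t with n₁ + n₂ − 2 degrees of freedom and noncentrality d·√(n₁n₂/(n₁ + n₂)) gives 80% power.

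| Split within D | Detectable d |
|---|---|
| 15/15 (30 in D) | 1.06 SD |
| 11/12 (23 in D) | 1.23 SD |
| 11/11 (22 in D) | 1.26 SD |

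The normal approximation gives the same picture: (1.960 + 0.842) × √(1/15 + 1/15) = 1.02 SD with 30, against 1.18 SD with 22.5.

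**5. Effect on between-arm comparisons.** The standard error is proportional to √(1/n₁ + 1/n₂).
- D versus A: √(1/20 + 1/30) = 0.289 as planned; √(2/22.5) = 0.298 with equal arms, about 3% worse.
- A versus B: √(2/20) = 0.316 as planned; 0.298 with equal arms, slightly better.

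**6. Size of the improvised remedy.** If A to C were capped at 20 under balanced allocation, the first 80 would fill all four arms to 20 and the last 90 − 80 = 10 could go only to D. With simple randomisation and caps of 20/20/20/30 (40,000 simulated trials), the mean number who could go only to D is 6.8, with 5th–95th percentile 0–16.

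**7. Does the alternative ratio deliver the plan?**
- 2:2:2:3 of 90: 90 × 2/9 = 20 and 90 × 3/9 = 30, exactly the planned sizes.
- With blocks of 9 in two strata, either all blocks are complete (20/20/20/30) or nine are complete and 9 participants fall in two part-blocks. Nine complete blocks hold 27 in D and 18 in each of A to C. The part-blocks add 0 to 6 to D and 0 to 4 to each other arm.
- So D is 27–33 and each of A to C is 18–22. In simulation, D is 29–31 in about 93% of trials (20,000 runs at each assumed impairment prevalence of 20%, 30% and 50%).

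**The case against.** The strongest reply is that this is one line of wording in a pilot with no stated power. Equal allocation slightly improves the comparisons among A, B and C, and costs the comparisons with D only 3% in standard error. Hypothesis 7 is a non-randomised contrast within one arm, and its inside/outside split is not controlled. With the full 30 in D but a 6/24 split, the detectable difference is about 1.33 SD, worse than the 1.23 SD that equal allocation gives with an even split. At an assumed difference of 0.5 SD, power is about 26% with 15/15 and 21% with 11/12, so the test is weak either way. The capping scenario is conjecture, and the document does not say which of its two statements governs.

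Much of this stands. No stated power is lost, correcting the ratio does not make hypothesis 7 well powered, and the capping figures describe something that might happen. Two further points about the remedy also stand: a fixed, known block length at a single site makes later assignments in a block partly predictable, and the number already randomised, and at what ratio, is not given.

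It does not remove the contradiction. The sample-size paragraph sets 30 for a stated purpose, its arm sizes add to a total given three times, and only the ratio in 2.D disagrees. Pilot status does not excuse an allocation instruction that cannot produce the planned arms.

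**Conclusion.** The concern holds and should be fixed. As written, 2.D yields 22 or 23 in arm D under balanced allocation, 25% below the planned 30. Equal allocation reaches 30 only by chance under simple randomisation (4.7%), and not at all with blocks of 4 or 8 within strata. The contradiction itself rests on document figures alone.

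The practical size is modest. Between-arm precision hardly moves. For hypothesis 7 the detectable difference grows from 1.06 SD to 1.23–1.26 SD, which depends on the assumed test, power and even split. The risk from capping arms A to C is real only if staff adopt that undocumented route. The ratio is the more natural statement to correct, because the arm sizes carry a reason and agree with the total.

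**What to change.** **In 2.D:** state the allocation as 2:2:2:3 (A:B:C:D), using permuted blocks within the two neurocognitive-impairment strata. Block lengths should be multiples of 9. It is better to vary the length, or to keep it in a document that site staff do not see; mixing 9 and 18 loosens the final arm sizes a little. State that nobody is assigned outside the randomisation list and that no arm closes because it has reached a count.

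**In the sample-size paragraph:** describe 20/20/20/30 as approximate targets, since incomplete blocks can move an arm by a few.

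**If participants have already been randomised 1:1:1:1** (the section on the pillbox fault shows participants on study in July 2018, but not how many had been randomised): record the date of the change, keep all four arms open at an unequal ratio favouring D for the rest, and accept the resulting sizes. As illustration, switching to 1:1:1:2 after m balanced assignments gives D = m/4 + (90 − m) × 2/5 and each of A to C = m/4 + (90 − m)/5:

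| m | A, B, C each | D |
|---|---|---|
| 40 | 10 + 10 = 20 | 10 + 20 = 30 |
| 60 | 15 + 6 = 21 | 15 + 12 = 27 |
| 80 | 20 + 2 = 22 | 20 + 4 = 24 |

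Allocation period should then enter the between-arm analysis in Statistical Considerations (item 12).

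If the sponsor prefers equal arms, the sample-size paragraph must be rewritten instead, including its justification for hypothesis 7.

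**Cost:** one sentence in each of two sections and a new allocation list, with the total unchanged at 90. Arms A to C have about 20 rather than 22 or 23, final sizes are approximate, and a mid-trial change adds a period term and an amendment to the analysis text.
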